If the patient meets all eligibility criteria, they will be consented by study staff members and then randomized to receive ketamine 0.25mg/kg in 100cc normal saline (NS), up to a

maximum of 30mg total dose, as an IV infusion over the specified time, as well as “placebo” 100cc NS over the other time slot.

[figure not shown]
If during the baseline assessment, immediately prior to the start of infusion, the subject reports an improved pain score (VAS < 5 cm(50mm)), the subject will be considered no longer eligible. The infusion will not be administered, and the subject will be removed from the study.

Since the subject was randomized, the group allocation (control or experimental group) for that subject will be reassigned to the randomization block to maintain a total of 48 enrolled (infused) subjects.

Pharmacy staff will provide the study medication in a blinded fashion to the nurse who will use infusion pumps to deliver both study medication and placebo simultaneously. Nursing staff will receive training on administration of the study medication prior to starting the study.

We will measure the side effect profile using the Side Effects Rating Scale for Dissociative Anesthetics (SERSDA) along with the Visual Analog Scale (VAS) (Appendix A).

Visual Analogue Scale scoring is done by asking the subject to mark the spot on the VAS Pain Assessment Tool (0-10cm) to indicate their perception of pain. Following this, the investigator scores the intensity of pain according to the 0-100mm corresponding scale (one instrument i.e., 5cm= 50mm). The VAS is a validated, subjective measure for acute and chronic pain. See below for exact tool that will be used.

Vital signs (heart rate, blood pressure, respiratory rate, and oxygen saturation) will also be obtained at 0, 5, 15, 30, 60, and 90 minutes from the start of the ketamine/NS placebo infusion.

Ketamine 30 min vs 15 min

Version: 7

Date: 06.06.2024

Page 7 of 15

Rescue Medication

At 30, 60 or 90 minutes post start of the ketamine infusion, if the study subject has a VAS score that is between 5-10cm (50-100mm), a **single** dose of both acetaminophen 1,000mg (oral) and ketorolac (15-30mg IV) will be given. If alternative medications are required, the study investigator will be consulted.

NOTE: EPIC recommends a ketorolac dose of 15mg IV if subject weight is less than 50kg or subject age is ≥ 65 years.

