3.1 Subject Population

Inclusion and Exclusion Criteria

Ketamine 30 min vs 15 min

Version: 7

Date: 06.06.2024

Page 8 of 15

Inclusion criteria:

- Patients 18 years of age or older
- Primary complaint of acute moderate to severe pain on VAS/numeric pain scale (a score of ≥ 5 cm which corresponds to 50mm).
- Pain described as abdominal, flank, back, musculoskeletal, or traumatic chest pain
- Must be alert and oriented times three
- Able to provide informed consent.

Exclusion criteria:

- Pregnant
- Breastfeeding
- Altered mental status
- Known or reported allergy, hypersensitivity, or intolerance to ketamine
- Unstable vital signs (systolic blood pressure < 80 or > 180 mmHg, heart rate < 50 or > 150 beats per minute, and respiratory rate < 10 or > 30 breaths per minute)
- History of unstable heart disease, such as arrhythmias, congestive heart failure, or coronary heart disease.
- History of untreated or uncontrolled thyroid disease
- Acute head or eye injury
- Active or current abuse of alcohol or illicit drugs
- Known intracranial hypertension
- Hepatic or renal insufficiency
- Current active manic phase of bipolar disorder
- Active delusions, hallucinations, or schizophrenia
- Patients who have recent fentanyl use within 60 minutes or other analgesic use (opiates) within 4 hours of study enrollment (signing of consent)
- Patients who have enrolled in the study during a previous ED encounter
- Chronic use of opiates (i.e.: fentanyl patch, SR opiates)

It will be at the discretion of the treating ED physician who is taking care of the patient to determine whether the patient is appropriate for the study. If it is determined the patient requires a more urgent form of pain control intervention, the patient will be excluded.

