3.2 Study Intervention

Once consented, participants will be randomized to receive 0.25mg/kg (up to a maximum

Ketamine 30 min vs 15 min

Version: 7

Date: 06.06.2024

Page 9 of 15

of 30mg) intravenous ketamine mixed with 100cc normal saline (NS) either over: (1) 15-minute slow infusion (SI) or (2) 30-minute slow infusion.

Each group will receive corresponding placebo of 100cc NS for double dummy design.

The group receiving ketamine over 15-minute SI, will also receive 100cc NS over 30 minutes and the group receiving ketamine over 30 min SI will also receive 100cc NS over 15 min. Ketamine/NS placebo infusions will be delivered via infusion pump. The two infusions are to be given simultaneously so that time zero (0) is the same for both infusions.

Ketamine/NS placebo will be prepared and blinded by pharmacy staff and be administered in a blinded fashion by an ED or Research RN. For the purposes of this study a subject will be considered enrolled once they have received any portion of the investigational product.

Patients may not be enrolled in the study more than one time. They may not be re-enrolled if they present to the ED with acute pain a subsequent time. This is to prevent any bias from forming in the data analysis secondary to the side effect profile of the drug as well as the potential psychotropic effect the drug may have.

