The sample size of n=24 in each study arm (n=48 overall) was determined to detect a clinically significant median change of one unit in the primary outcome and SERDSA scale, for measuring adverse events. This determination assumes the same standard deviation of 1.2 units with 80% power assuming a two-sided alpha type I error rate of 5% used previously to adequately power the Motov study² which was based on the estimated standard deviation from the Andolfatto¹⁶ study. We will enroll stratified by gender (male/female) to ensure equality between the two study groups.

Separate sealed envelopes will be provided to the pharmacist containing the randomization assignment to allow for more comparability between study arms. Each sealed envelope will be identified by gender and patient enrollment number, e.g., 'Male 01', and contain an assignment to either study arm within the envelope. Envelopes for randomized subjects will be stored in the investigational pharmacy. A secondary copy of the randomization assignments will be managed on a secure research shared drive within the Clinical Research Center. Access will be limited to only unblinded study staff. A

Ketamine 30 min vs 15 min

Version: 7

Date: 06.06.2024

Page 11 of 15

maximum enrollment for either gender will be 14 out of the 24 (58.3%) to provide a more balanced gender ratio which is more generalizable to the intended population.

Randomized blocks of 2 and 4 units will be employed within each gender strata to allow for balance across the enrollment period.

Study data will be collected via a REDCap instrument. A randomization number will be assigned and after baseline data is collected, observation and longitudinal data will be captured via a repeated measures survey in REDCap. Time points captured will be baseline (0min), 5min, 15min, 30min, 60min and 90min from the start of the study infusion which is time zero.

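### The arm of a subject removed after randomization but before infusion goes back into the block for re-use, a small risk to allocation concealment that taking the next sealed envelope would avoid

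*Combined protocol and SAP*

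**What the plan says.** Under section 3 (Study Design) a subject is consented, then randomized, and pharmacy supplies the blinded bags. The pain score is then checked once more. If, "immediately prior to the start of infusion, the subject reports an improved pain score" below 5 cm (50 mm), the infusion is withheld and the subject leaves the study. The protocol notes that this person has already been randomized and adds that "the group allocation (control or experimental group) for that subject will be reassigned to the randomization block". The stated aim is a final count of 48 people infused.

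Section 4 (Data Analysis/Plan) describes the randomization. "Separate sealed envelopes will be provided to the pharmacist containing the randomization assignment". "Each sealed envelope will be identified by gender and patient enrollment number", for example Male 01. "Randomized blocks of 2 and 4 units will be employed within each gender strata". Envelopes of randomized subjects are kept in the investigational pharmacy, and a second copy of the assignments is open only to unblinded study staff.

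Three other statements bear on the point:

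- Section 3.2 (Study Intervention) says that "a subject will be considered enrolled once they have received any portion of the investigational product", so a subject removed at the re-check is randomized but never enrolled.
- Section 3 calls the trial intent to treat.
- Section 4 leaves people who withdraw before medication out of the final data set. Only later withdrawals are said to appear on the diagram.

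**The concern.** Sealed envelopes exist so that nobody handling the next assignment knows it in advance. Someone in pharmacy must know which bag holds ketamine, so by the time of the bedside re-check that subject's envelope would normally be open. If the arm then goes back into the block, at least one assignment still to be given out is already known in pharmacy. The protocol does not say how, when or by whom the returned arm is re-issued.

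Two things are at stake. The first is concealment. Whether a patient enters involves judgement (section 3.1: "It will be at the discretion of the treating ED physician" to decide on suitability), and an assignment known in advance matters if that knowledge reaches anyone who influences entry. The second is reporting. Once the arm has passed to another person, the plan does not say that removed subjects will be shown by the arm they were first given. A reader could then not check that removals after randomization were balanced.

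**Working it through.** **1. What the text establishes.**

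| Step | Source | Stated or inferred |
|---|---|---|
| Removal comes after randomization | Section 3 | Stated |
| The arm returns to the block | Section 3 | Stated |
| Assignments are in sealed envelopes given to the pharmacist | Section 4 | Stated |
| The envelope is open by the time of the re-check | Sections 3, 3.2 and 4 | Inferred; normal if pharmacy is to prepare the bags |
| The arm goes to the next patient of the same gender | – | Not stated; possible, since numbers may count only enrolled (infused) subjects |
| Recruiters learn the arm | – | Not stated |
| Unblinded staff are kept out of screening and consent | – | Not stated |

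**2. How often it could happen.** The documents give no removal rate, so everything in this step is assumption. Entry needs at least 50 mm (section 3.1) and removal is below 50 mm (section 3), so the two share one line. Take screening VAS as uniform from L to 100 mm and the change to re-check as normal with mean m and SD s. Ignoring the negligible or small upper tail, with z = (L − 50 + m)/s,

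removal rate = s × [φ(z) − z × Φ(−z)] / (100 − L).

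- L = 50, m = 0, s = 10: 10 × 0.399 / 50 = 8.0%.
- L = 50, m = −5, s = 10: z = −0.5; 10 × (0.352 + 0.5 × 0.691) / 50 = 14.0%.
- L = 50, m = 0, s = 5: 5 × 0.399 / 50 = 4.0%.
- L = 50, m = −5, s = 15: z = −0.333; 15 × (0.377 + 0.333 × 0.631) / 50 = 17.6%.
- L = 60, m = 0, s = 5: z = 2; 5 × (0.0540 − 2 × 0.0228) / 40 = 0.1%.
- L = 60, m = −5, s = 15: z = 0.333; 15 × (0.377 − 0.333 × 0.369) / 40 = 9.5%.

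The range is about 0% to 18%. The expected number of the 48 slots affected is 48 × rate: from 48 × 0.001 = 0.05 to 48 × 0.176 = 8.5.

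**3. The plan's own sample size.** Inputs from section 4: difference 1, SD 1.2, two-sided 5%, 80% power. By the normal approximation n = 2 × (1.960 + 0.842)² × 1.2² / 1² = 22.6, so 23 per arm. The two-sample t-test gives 23.6, so 24 per arm, the stated figure.

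**4. What it costs not to re-use the slot.** The t-test noncentrality is 1 / (1.2 × √(1/n₁ + 1/n₂)) with 46 degrees of freedom.

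| Final split | Noncentrality | Power |
|---|---|---|
| 24/24 | 2.887 | 80.7% |
| 25/23 | 2.884 | 80.6% |
| 26/22 | 2.877 | 80.4% |
| 27/21 | 2.864 | 80.1% |

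Simulating the next-sealed-envelope rule (two gender strata, random blocks of 2 and 4, recruitment until 48 are infused) at an assumed 10% removal gives a mean absolute arm difference of about 1.9 subjects, a 95th percentile of 4, and mean power of 80.6%. A second simulation assumed 24 infused subjects per gender and removal of 2% to 20%. It gave mean differences of 0.9 to 2.6, and average power stayed within about 0.2 points of the 24/24 value.

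**The case against.** The strongest reply is that nobody who decides on entry is shown to learn anything. Consent comes before randomization, the nurse works blinded, and the second list is limited to unblinded staff. Those holders can already see every future assignment, so re-use tells them nothing new. The treating physician, whose discretion section 3.1 describes, has no documented access to the envelopes, and pharmacy has no documented say in who enters. All of this stands, and it is why the risk is limited. What it leaves open is the dispensing pharmacist, for whom the seal is a safeguard and who would know a returned arm early, and the absence of any rule keeping unblinded staff out of screening or consent.

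A reader might infer more than the documents support:

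- *The next patient of that gender is assigned from the opened envelope.* Returning an arm to the block also fits a new sealed envelope or a later position. Storage of randomized subjects' envelopes points, if anything, away from physical re-use. Section 3 also contains a figure that could not be read here and might add detail.
- *The removed subject has no arm on record.* Nothing says the assignment is erased, and section 4 provides for stored envelopes and a second copy. The gap is only that no section provides for reporting these subjects by arm.
- *Re-use makes the rest of a small block guessable.* Any opened envelope in a block of 2 or 4 narrows what remains, whether or not that subject is infused.

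It is also fair to say that re-use helps keep the planned 24/24. The power table shows how little that is worth.

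**Conclusion.** The point holds as a cheap improvement. The protocol states a rule under which a pending assignment may be known to the dispensing pharmacist before the next patient is randomized, and it makes no provision for showing randomized-but-not-infused subjects by arm in a trial it calls intent to treat. It would go too far to say that allocation concealment is lost for the slot: concealment concerns those who decide on entry, and no section gives them the arm.

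The size is uncertain. The range of 0% to 18% removed rests wholly on assumed VAS distributions, and it counts slots exposed to re-use, not bias. No effect on the SERSDA comparison has been estimated. The finding that re-use is unnecessary is firmer. It rests on the plan's own difference and SD, with a t-test standing in for the planned gamma model, and varies little over the removal rates tried. Removing such subjects is not itself criticized, since the check precedes dosing and is made under blinding.

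**What to change.** Replace the re-use sentence in section 3 with:

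> A subject removed before infusion keeps the assigned envelope and arm on record. The next eligible subject of that gender receives the next sealed envelope, and spare blocks are added to each gender list so that 48 subjects are infused.

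Add two statements: that removed subjects are shown by assigned arm in the flow diagram, and that unblinded staff take no part in screening or consent.

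The cost is a few protocol sentences and some extra envelopes per gender list. The downside is that the arms may finish slightly unequal, for example 25/23 or 26/22, which lowers power by 0.1 or 0.3 percentage points (80.7 − 80.6; 80.7 − 80.4).

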3.1 Subject Population

Inclusion and Exclusion Criteria

Ketamine 30 min vs 15 min

Version: 7

Date: 06.06.2024

Page 8 of 15

Inclusion criteria:

- Patients 18 years of age or older
- Primary complaint of acute moderate to severe pain on VAS/numeric pain scale (a score of ≥ 5 cm which corresponds to 50mm).
- Pain described as abdominal, flank, back, musculoskeletal, or traumatic chest pain
- Must be alert and oriented times three
- Able to provide informed consent.

Exclusion criteria:

- Pregnant
- Breastfeeding
- Altered mental status
- Known or reported allergy, hypersensitivity, or intolerance to ketamine
- Unstable vital signs (systolic blood pressure < 80 or > 180 mmHg, heart rate < 50 or > 150 beats per minute, and respiratory rate < 10 or > 30 breaths per minute)
- History of unstable heart disease, such as arrhythmias, congestive heart failure, or coronary heart disease.
- History of untreated or uncontrolled thyroid disease
- Acute head or eye injury
- Active or current abuse of alcohol or illicit drugs
- Known intracranial hypertension
- Hepatic or renal insufficiency
- Current active manic phase of bipolar disorder
- Active delusions, hallucinations, or schizophrenia
- Patients who have recent fentanyl use within 60 minutes or other analgesic use (opiates) within 4 hours of study enrollment (signing of consent)
- Patients who have enrolled in the study during a previous ED encounter
- Chronic use of opiates (i.e.: fentanyl patch, SR opiates)

It will be at the discretion of the treating ED physician who is taking care of the patient to determine whether the patient is appropriate for the study. If it is determined the patient requires a more urgent form of pain control intervention, the patient will be excluded.

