At 30 minutes post start of ketamine infusion, if the study subject has a VAS score that is between 8-10cm (80-100mm), fentanyl will be administered at 1mcg/kg up to 100mcg. (The dose will be calculated by EPIC to correspond to the nearest 0.05cc). If deemed safe and appropriate, the EPIC alert for doses greater than 100mcg may be overridden by the treating physician or study investigator to authorize doses greater than 100mcg (per institutional policy).

If the VAS score remains 8-10cm (80-100mm)) when assessed at 60 and 90 minutes post start of the ketamine infusion, the fentanyl dosing may be repeated.

NOTE: If the VAS score is assessed to be between 8-10cm (80-100mm) at any time point, and ketorolac and acetaminophen have **not** already been administered, ketorolac, acetaminophen and fentanyl may be given at the same time point.

NOTE: Ketorolac and acetaminophen may only be administered once during the study.

Study Termination

If rescue medication is administered, the patient will continue in the study and all data will be collected as outlined in the protocol as ITT (intent to treat).

If the subject experiences side effects which are unable to be managed in order to permit the continuation of the ketamine infusion, it will be stopped. All data will continue to be collected according to the protocol and the subject will continue to be observed for the remainder of the 90-minute study period, unless the subject withdraws their consent to participate.

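### Analgesics still taking effect at time 0 are neither fully excluded nor among the listed variables, so they can count toward pain criteria that have no ketamine-free comparator

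*Combined protocol and SAP*

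**What the plan says.** **Exclusion.** Section 3.1 excludes "Patients who have recent fentanyl use within 60 minutes or other analgesic use (opiates) within 4 hours of study enrollment (signing of consent"). The only other analgesic exclusion is "Chronic use of opiates (i.e.: fentanyl patch, SR opiates"). Nothing in the list concerns NSAIDs or acetaminophen.

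**Enrolment.** Section 3.1 equates enrolment with signing consent. Section 3.2 says "a subject will be considered enrolled once they have received any portion of the investigational product". Randomisation and pharmacy preparation fall between these two points.

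**Check before infusion.** Section 3 has one: "If during the baseline assessment, immediately prior to the start of infusion, the subject reports an improved pain score" (below 50 mm), the subject is removed. No second check of analgesic use is described.

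**Rescue.** Acetaminophen plus ketorolac is triggered as follows: "At 30, 60 or 90 minutes post start of the ketamine infusion, if the study subject has a VAS score that is between 5-10cm". A later note adds: "Ketorolac and acetaminophen may only be administered once during the study".

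**Data.** The variable list in Section 4 contains time to rescue analgesia but not analgesics taken earlier. In the Section 3.3 schedule, VAS is scored at time 0 and SERSDA first at 5 minutes.

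**Pain criteria.** Sections 1 and 3.3 define adequate control as VAS of 50 mm or less. Section 5 stops the study if 75% of subjects lack a 13 mm improvement.

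**The concern.** Ketorolac and acetaminophen are the plan's own rescue drugs, so the plan treats them as active analgesics. A patient who received either one shortly before time 0, or an opioid after consent, and who still marks 50 mm or more passes every stated check. Relief that develops over the next 30 minutes is then counted with whatever ketamine achieves.

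Three readouts are exposed because both arms receive ketamine: the share at 50 mm or less at 30 minutes, the need for rescue, and the 13 mm count behind the stopping rule. The stopping rule matters most, because carry-over could keep the trial running when ketamine alone would have triggered a stop.

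There is a smaller issue for the primary outcome. With no SERSDA score at time 0, fatigue or dizziness from an opioid given after consent cannot be told apart from a ketamine effect.

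**Working it through.** **Inputs from the documents.** 24 subjects per arm, SERSDA difference of 1 unit, SD 1.2, 80% power, two-sided 5% (Section 4); 13 mm criterion, 75% stopping threshold, reviews at 3, 6, 12, 24 and 40 patients (Section 5).

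**Plan's own figure.** n per arm = 2 × (1.96 + 0.84)² × 1.2² / 1² ≈ 22.6, so 23 by the normal approximation. The t-test needs 23.6, so 24, with 80.7% power at 24. The stated size reproduces; this point does not depend on it.

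**Who can be infused under the text**

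| Analgesic and timing | Stated exclusion | Pain check at time 0 |
|---|---|---|
| Opioid before consent, inside the window | Excluded | – |
| Opioid after consent | Not covered by the consent anchor | Removes only VAS below 50 mm |
| Ketorolac or acetaminophen, any time before time 0 | None | Removes only VAS below 50 mm |

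**Assumed inputs.** The documents give no pre-treatment rate or carry-over effect for this population, so everything below is illustrative.

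*1. Mean improvement.* Inflation = share pre-treated × mm gained after time 0.
- Low: 0.2 × 10 = 2 mm, and 2/13 = 15% of the plan's criterion.
- High: 0.5 × 15 = 7.5 mm, and 7.5/13 = 58%.

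This gives the full gain to every pre-treated subject. A drug already at full effect lowers the time-0 score and adds nothing to the change afterwards, so the range leans high.

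*2. Stopping rule.* Assume a proportion q reaches 13 mm on ketamine alone, 60% do so with a prior analgesic, and a share s is pre-treated. The overall responder rate is p = q(1 − s) + 0.6s. The chance of stopping at one review of N subjects is the binomial probability that at least 0.75N are non-responders (18 of 24, 30 of 40).

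| q | s | p | N = 24 | N = 40 |
|---|---|---|---|---|
| 0.2 | 0 | 0.20 | 0.81 | 0.84 |
| 0.2 | 0.25 | 0.30 | 0.39 | 0.31 |
| 0.2 | 0.50 | 0.40 | 0.10 | 0.04 |
| 0.4 | 0 | 0.40 | 0.10 | 0.04 |
| 0.4 | 0.50 | 0.50 | 0.01 | 0.001 |

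These are single-review probabilities. The effect is large when ketamine alone works poorly, which is when the rule is meant to act, and small otherwise.

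*3. Between arms.* With 30% pre-treated, the SD of the difference in shares is √(2 × 0.3 × 0.7 / 24) = 0.132. Multiplied by 10–15 mm, that is 1.3–2.0 mm at one SD. A gap of 6 subjects is 6/24 = 25 points, or 2.5–3.75 mm. The SD of the difference in counts is √(2 × 24 × 0.3 × 0.7) = 3.17, so 6 is 1.9 SD; the exact chance of a gap of 6 or more in either direction is 8%.

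*4. SERSDA noise.* If residual drug moved SERSDA by d = 0.5–1 point in a share s = 25–50%, SD = √(1.44 + s(1 − s)d²) = 1.22–1.30, and power at 24 per arm would be 74–79% instead of 80.7%. Shares that high would be extreme for opioids given after consent.

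**The case against.** Much of the case on the other side stands.

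- **Arm comparison.** A reader might infer that prior analgesics bias or dilute the 15 versus 30 minute contrast. Allocation is randomised and double-blind, so there is no systematic bias, and an additive shift common to both arms leaves the difference unchanged. Dilution would need a floor effect or an interaction, and the documents support neither. The chance shift is well under 13 mm.
- **Consent anchor.** For doses before consent it is conservative, because time 0 comes later. The timing gap concerns only doses given after consent. No section provides for such doses, and Section 3.1 has a partial safeguard: "If it is determined the patient requires a more urgent form of pain control intervention, the patient will be excluded". Nothing bars or re-checks them, however.
- **Rescue text.** A reader might infer that the sections contradict each other on pre-study ketorolac or acetaminophen. They do not: the exclusion list never mentions these drugs, and the single-dose and once-only statements agree. The text is silent on earlier doses, and the note asking whether the drugs have already been given can be read either way.
- **Recording.** The Section 4 list is introduced as what the variables include. It also omits interventions for side effects, which Section 3.3 says are monitored. Prior analgesics may therefore be captured, but the plan does not say so.
- **Attribution.** Section 5 asks whether a reduction occurred, not what caused it. Natural course and expectation are also in that count, and this fix does not remove them.
- **Prevalence.** Section 2 cites a case series in which 13 of 14 patients had prior analgesia. That is another population with the drug type unstated, so it cannot set a rate here.

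Allowing prior non-opioids is a legitimate design choice. Leaving them off the stated data and analysis plan is the weakness.

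**Conclusion.** The gap holds on the text. The exclusion names opioids only and is anchored at consent, a later definition of enrolment exists, the pain score is the only stated check immediately before infusion, and prior analgesics are not listed as data. An analgesic still taking effect after time 0 can therefore count toward the 30-minute VAS result, the need for rescue and the 13 mm rule, with no stated means of seeing it.

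The size is uncertain. The 2–7.5 mm inflation and the stopping probabilities rest wholly on assumed pre-treatment rates and effects. The documents do not support reading this as a threat to the validity of the randomised comparison, for either SERSDA or VAS: there it is noise and chance imbalance, about 1–2 mm on VAS at one SD. This is a cheap improvement to what the absolute pain criteria can show.

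**What to change.** 1. Reconcile the enrolment anchors in Sections 3.1 and 3.2 so that it is clear whether the existing exclusion applies up to time 0, and check analgesic use alongside the baseline VAS.
2. Record drug, dose and time of every analgesic given before time 0, and tabulate by arm.
3. Pre-specify prior analgesic (yes/no) as a covariate in the pain model. A dose given between randomisation and time 0 precedes study drug and is given under blinding, so adjusting for it is acceptable.
4. Repeat the 30-minute VAS result and the 13 mm count without pre-treated subjects. At an assumed 30% pre-treated this leaves about 0.7 × 24 ≈ 17 per arm, so treat it as descriptive.
5. Clarify in the Rescue Medication text whether ketorolac or acetaminophen given before the study counts toward the once-only rule.

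Which washout or rescue rule is right is the sponsor's clinical decision, and none is proposed here.

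Cost: clarified wording, a few REDCap fields, one extra analysis and possibly a few subjects lost at the time-0 check.
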